6.3.3 Study Procedures

The Study Visit Schedule is outlined in Table 4 for enrolled subjects for the duration of the study from Screening and Baseline through the 30 Day visit (Primary Endpoint) and 5 year follow-up visits.

| | Screening | Baseline (≤30 days of procedure) | Procedure | Post-Procedure (Within 48 hours) | Discharge | 30 Day Follow-Up (+14 days) | 6 Month (+/-30 days) | 1 Year (+/-60 days) | 2-5 Years (+/-60 days) |
|--|-----------|-------------------------------------|-----------|-------------------------------------|-----------|--------------------------------|----------------------|---------------------|------------------------|
| Informed Consent | Х | | | | | | | | |
| Medical History | Х | | | | | | | | |
| Physical Exam | Х | | | | Х | Х | | Х | Х |
| CSS Angina | Х | | | | Х | Х | | Х | Х |
| NYHA Classification | Х | | | | Х | Х | | Х | Х |
| STS Risk Score, Logistic EuroSCORE, and EuroSCORE II | х | | | | | | | | |
| Operability Risk Assessment | х | | | | | | | | |
| Cardiac Medications | | Х | Х | Х | Х | Х | Х | Х | Х |
| Adverse Event Assessment ¹ | | | х | х | х | х | х | х | х |

Table 3 Study Visit Schedule

7 February 2017, Version 2.0

| Frailty Assessment | | Х | | | | | | |
|---|---|----------------|--------|----------------|----------------|----------------|-----------------------|-----------------------|
| NIH Stroke Scale | | X ² | | X ² | X ² | X ² | | |
| Modified Rankin Scale | | X ² | | X ² | X2 | X ² | | |
| Six Minute Walk Test (6MWT) | | х | | | | х | | |
| | | | Lab | S | | | | |
| Hemoglobin, Hematocrit, Platelet Count and White Blood Cells | | х | | х | х | х | | |
| PTT or PT/INR | | Х | | Х | Х | | | |
| CK/CK-MB and/or Troponins | | X ³ | | X4 | | х | | |
| Creatinine | | Х | | Х | Х | Х | | |
| Liver Panel (ALT, AST) | | Х | | | | | | |
| Albumin | | Х | | | | Х | | |
| | | Non | Invasi | ve Tests | | | | |
| ECG | | Х | | Х | Х | Х | Х | |
| Chest X-ray | | Х | | | | | | |
| Transthoracic Echocardiogram (TTE) ⁶ | х | | | | х | х | х | х |
| Fluoroscopic imaging implanted valve | | | х | | | X ⁵ | X ⁵ | X ⁵ |
| | | In | vasive | Tests | | | | |
| CT Thoracic/Abdomen with visualization of iliac and femoral arteries | x | | | | | | | |
| Cardiac Catheterization or CT angiogram | х | | | | | | | |
| Supra-aortic Angiogram or (TEE) | х | | х | | | | | |
| Invasive hemodynamics | | | х | | | | | |

¹ Collection of adverse events begins when the patient starts the procedure. This is defined as when anesthesia is first administered

²A neurologist or a neurology fellow will assess patients at Baseline, Post Procedure and Discharge. If the neurologist or neurology fellow is not available at the time of patient's baseline or discharge visit, a certified team member may perform the tests. A neurologist or neurology fellow must perform the Post Procedure assessment.

³ Baseline CK/CKMB and/or Troponins are required 2 72 hours before the procedure.

⁴Post Procedure CK/CKMB and/or Troponins are required at 3 different time intervals: 1) the first lab draw post procedure (within 8 hours of exiting the cath lab or operating room) 2) the second lab draw 6 - 8 hours after the first lab draw 3) the third lab draw 6 - 8 hours after the second lab draw.

⁵For patients with abnormal findings related to valve integrity and position and patients with Adverse Events related to worsening valve function.

⁶Transesophogeal Echocardiogram (TEE) may be used if TTE is not available

6.3.3.1 Screening

The following screening data will be collected for all study patients to assess eligibility as per standard of care:

- Operability Risk Assessment
- Medical history, pertinent physical examination [include blood pressure, height, weight and all major systems findings]
- NYHA functional classification
- CSS Angina classification
- Risk assessment (STS Risk Score, Logistic EuroSCORE, and EuroSCORE II)

Non-Invasive Studies (must be completed within 60 days before procedure date)

• Comprehensive transthoracic echocardiogram (TTE) (transesophageal echocardiogram (TEE) may be used as an alternative)

Invasive Studies (must be completed before the procedure date)

- Cardiac and abdominal CT angiogram with visualization of the aortic arch, both iliac and femoral arteries to the aorta. In the situation where patients have compromised renal function that precludes the use of contrast agents, MR imaging may be used as an alternative to CT (≤180 days before procedure)
- Left heart catheterization to assess the severity of aortic stenosis and severity of coronary artery disease (≤180 days before procedure)

If any assessments need to be completed or repeated outside of standard of care, a patient will need to sign a Patient Informed Consent prior to completing assessments.

6.3.3.2 Baseline

Assessments and laboratory tests are required to be completed within 30 days prior to the procedure date. Assessments and laboratory tests completed outside of the 30 days will need to be repeated. If completed outside of standard of care, then a Patient Informed Consent Form will need to be signed first.

The following Baseline data will be collected for all study patients prior to procedure:

- Current cardiac medications and all medications given for cardiovascular effect;
- Neurological assessment (Appendix A)
 - o NIHSS
 - o MRS
- Frailty Assessment (Appendix B)

- Six Minute Walk Test (Appendix C)
- Clinical Laboratory Tests
 - Blood count (hemoglobin, hematocrit, platelet count, white blood cells)
 - PTT or PT/INR
 - CK/CK-MB and/or Troponins
 - Creatinine
 - Liver Panel (ALT, AST)
 - o Albumin
- Non-invasive studies
 - o 12-Lead ECG
 - Chest x-ray
- Adverse Event Assessment

6.3.3.3 Procedure

Transfemoral access technique will be used by the investigator in his/her normal practice of interventional cardiology and patient selection process.

6.3.3.3.1 Recommended Antiplatelet/Anticoagulation Regimen

Table 5 outlines the recommended antiplatelet regimen. The categories were developed by The PARTNER II Trial Patient and Procedure Management Steering Committee. There are no current validated guidelines in this specific study population, however, the literature was surveyed and used as guidance for the following proposed guidelines. It is expected that specific agents and dosing regimens may vary from site to site. Patients will be assessed by the heart team for Category of Stroke Risk prior to prescribing treatment regimen. The Category and specific treatment regimen will be documented in the discharge case report form. Committee Categories are based on CHADS 2 score for stroke risk [40].

NOTE: The CHADS 2 score only applies to patients in atrial fibrillation (AF) and has not been validated in non-AF patient populations; therefore the CHADS 2 score reference was used as one among many guidelines to establish the risk stratification for intensity of anticoagulation regimen.

| Pre procedure | Aspirin 75-100 mg once daily |
|---------------|--|
| | Patients with bare metal stent (BMS) within one month or drug eluting stent (DES) within 12 months should be continued on Clopidogrel/Prasugrel prior to their procedure Patients in atrial fibrillation on warfarin should be bridged with |

Table 4 Summary of Recommended Antiplatelet/Anticoagulation Therapy

| | LMW or UF heparin prior to the procedure Patients with persistent or paroxysmal atrial fibrillation, not on anticoagulation, will not be required to have a TEE to rule out LA thrombus prior to procedure. If intra-procedural TEE during TAVI reveals thrombus, procedure will be aborted and delayed until patient has been on warfarin or dabigatran for 30 days. In patients under concomitant TAVI/PCI, Clopidogrel loading with either 300mg or 600mg prior to the procedure is recommended in addition to ASA: |
|---|--|
| Intra procedure | Heparin will be given to achieve/ maintain ACT > 250 sec. |
| Post procedure | |
| Category I for Stroke Risk No atrial fibrillation, No recent stents | ASA 75mg once daily Clopidogrel 300mg load within 6 hours of procedure (either pre or post) Clopidogrel 75mg once daily for at least one month post procedure |
| Category II for Stroke Risk No atrial fibrillation, recent stents | ASA 75mg once daily Clopidogrel 75mg once daily should be continued prior to the procedure and after the procedure without interruption for at least one month after BMS and 12 months after DES |
| Category III for Stroke Risk Atrial fibrillation, no recent stents | ASA 75mg once daily Patients should be started on warfarin or dabigatran 24 hours post TAVI if clinically safe and this should be continued for at least one month or indefinitely if possible. If clinically safe, patients started on warfarin should be bridged with unfractionated or low molecular weight heparin until INR therapeutic. If patients are not a candidate for warfarin or dabigatran, Clopidogrel 75mg once daily can be considered as an alternative |
| Category IV for Stroke Risk Atrial fibrillation, recent stents | ASA 75mg once daily Clopidogrel 75mg once daily for at least one month post BMS or 12 months post DES Patients should be started on warfarin or dabigatran 24 hours post TAVI if clinically safe and continued indefinitely. If |

clinically safe, patient's being started on warfarin should be bridged with UF or LMW heparin until INR therapeutic.

Note: Any changes to anticoagulation regimen from study visit to study visit will be noted on the CRF including reason for change.

6.3.3.3.2 Antibiotic Prophylaxis

Study subjects should be treated prophylactically with antibiotics for endocarditis per the recommendations of the American Heart Association [43].

6.3.3.3.3 Procedure Assessments

Procedural information, findings, results, and SAPIEN XT delivery system and device identification will be recorded on the Case Report Form and are listed below:

- Duration of the procedure, defined as the time from skin incision to access closure;
- All cardiac medications and all medications given for cardiovascular effect;
- A supra-aortic angiogram or TEE to assess valve performance and coronary patency
- Fluoroscopic imaging of implanted valve to assess acute deployment (e.g. proper annular placement, fully vs. under deployed, circularity/ovality)
- Contrast media quantity
- Total fluoroscopy time and dose
- Adverse events

Subjects will be continuously monitored clinically, hemodynamically, and electrocardiographically during the index procedure for all local and systemic side-effects.

It is recommended subjects are monitored in the operating room for at least 15 minutes after completion of the procedure, with special attention to hemodynamic condition and cardiac rhythm. The sheaths may be removed when ACTs reach <150 sec after implantation of the study valve (for non-surgical closures).

6.3.3.4 Post-Procedure

Post-procedure clinical evaluations should be performed within 48 hours of the index procedure. Specific assessments include the following:

- Current cardiac medications and all medications given for cardiovascular effect
- Adverse events
- Neurological assessment
 - NIHSS
 - o MRS

- Clinical Laboratory Test
 - Blood count (hemoglobin, hematocrit, platelet count, white blood cells)
 - PTT or PT/INR
 - CK/CK-MB and/or Troponins
 - o Creatinine
- 12-Lead ECG

6.3.3.5 Discharge Visit

The following data will be collected for all study patients before discharge from the index hospitalization. If patient is discharged over a weekend, the discharge tests may be completed on the last weekday prior to discharge. For patients that are discharged within the 48 hours of exiting the cath lab / operating room, it is not required to repeat tests collected during the Post Procedure period that are also required for the Discharge visit.

- Pertinent physical examination [include blood pressure, weight and all major systems findings]
- Current cardiac medications and all medications given for cardiovascular effect
- NYHA functional classification
- CSS Angina Classification
- Adverse events
- Neurological assessments
 - o NIHSS
 - o MRS
- Clinical Laboratory Test
 - o Blood count (hemoglobin, hematocrit, platelet count, white blood cells)
 - PTT or PT/INR
 - o Creatinine
- 12-Lead ECG
- Comprehensive TTE. If not adequate, a TEE will be performed

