| | problems associated with a device that relates to the rights safety or | |
| | welfare of patients. | |
| Acute Kidney Injury | Increase in serum creatinine (up to 7 days) compared with baseline | VARC-2 |
| | Stage 1: Increase in serum creatinine to 150% to 199% (1.5 to 1.99 | - |
| | increase compared with baseline) OR increase of 0.3 mg/dl (26.4 mmol/l), OR | |
| | Urine output < 0.5 ml/kg/hr for > 6 hours but < 12 hours | |
| | Stage 2: Increase in serum creatinine to 200% to 299% (2.0 to 2.99 | |
| | increase compared with baseline). OR | |
| | Urine output < 0.5 ml/kg/hr for > 12 hours but < 24 hours | |
| | Stage 3:* Increase in serum creatinine to 300% (3 increase compared with | |
| | baseline) or serum creatinine of 4.0 mg/dl (354 mmol/l) with an acute | |
| | increase of at least 0.5 mg/dl (44 mmol/l), OR | |
| | Urine output < 0.3ml/kg/hr for ≥ 24 hours OR anuria ≥ 12 hours | |
| | The Increase in creatinine must occur within 48 hours | |
| | *Patients receiving renal replacement therapy are considered to meet | |
| | Stage 3 criteria irrespective of other criteria. | |
| Aortic Prosthetic Valve | Prosthetic Valve Stenosis | VARC-2 |
| Dysfunction | | |

| Term | Definition | Reference/ |
|---|--|------------|
| | Prosthetic valve regurgitation: Mean aortic valve gradient ≥20 mmHg, EOA ≤0.9-1.1 cm2‡ and/or DVI<0.35, AND/OR moderate or severe prosthetic valve regurgitation* | |
| | * Refers to VARC-2 definitions listed in this table | |
| Bleeding Event | Life-threatening or Disabling Bleeding • Fatal bleeding (BARC Type 5), OR | VARC-2 |

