| Conduction Disturbances and Arrhythmias | Up to 72 h, continuous rhythm monitoring is recommended in order to maximize detection of arrhythmias Data elements to be collected should include: Baseline conduction abnormalities, paroxysmal or permanent atrial fibrillation (or flutter), and presence of permanent pacemaker* Implant-related new or worsened cardiac conduction disturbance (new or worsened first degree atrioventricular (AV) block, second degree AV block (Mobitz I or Mobitz II), third degree AV block, incomplete right bundle branch block, right bundle branch block, intraventricular conduction delay, left bundle branch block, including block requiring permanent pacemaker implant Persistent or transient high degree AV block. High grade AV block is persistent if it is present every time the underlying rhythm is checked New permanent pacemaker implantation, with precision of the indication and number of days post-implant of placement of new permanent pacemaker New-onset atrial fibrillation (or flutter)[†] Any new arrhythmia resulting in hemodynamic instability or requiring therapy. | VARC-2 |

| Term | Definition | Reference/ |
|-----------------------------|---|---------------|
| | | Justification |
| | * Type of permanent pacemaker should be recorded (e.g. defibrillator, | |
| | single versus dual chamber, biventricular) | |
| | within bespitalization that has the ECC characteristics of strial fibrillation | |
| | (or flutter) and lasts sufficiently long to be recorded on a 12 load ECC, or at | |
| | (of fuller) and lasts sufficiently long to be recorded on a 12-lead ECG, of at | |
| | t Therapy includes electrical/medical cardioversion or initiation of a new | |
| | medication (oral anticoagulation, rbythm or rate controlling therapy) | |
| Conversion to Open Surgery | Conversion to open stornetomy during the TAVI procedure secondary to | |
| (TAVI-related) | any procedure-related complications | VARC-2 |
| Coronary obstruction (TAVI- | Angiographic or echocardiographic evidence of a new partial or complete | VARC-2 |
| related) | obstruction of a coronary ostium either by the valve prosthesis itself the | VANC 2 |
| | native leaflets, calcifications, or dissection, occurring during or after the | |
| | TAVI procedure | |
| Device Malfunction | The failure of a device to meet any of its performance specifications or | ISO14155:2011 |
| | otherwise perform as intended. Performance specifications include all | |

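### For patients discharged within 48 hours, one early creatinine may be the only scheduled sample inside the kidney-injury time limits, so stage II/III injury can be under-detected.

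*Combined protocol and SAP*

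**What the plan says.** Section 6.3.3.4 states: "Post-procedure clinical evaluations should be performed within 48 hours of the index procedure". The list there includes creatinine, blood count, coagulation, 12-lead ECG and the two neurological scales. It sets a latest time and no earliest time.

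Section 6.3.3.5 lists most of the same tests again for the Discharge visit and then grants a waiver to anyone who goes home less than 48 hours after leaving the procedure area. In those cases "it is not required to repeat tests collected during the Post Procedure period that are also required for the Discharge visit".

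Table 3 (section 6.3.3) schedules creatinine at Baseline, Post-Procedure, Discharge and the 30-day visit. Under section 6.3.3.6 the 30-day visit may fall from day 30 to day 44. No visit is scheduled between discharge and day 30.

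Section 4.2 names stage II or III acute kidney injury at 30 days as a secondary safety endpoint. Section 10 defines the creatinine criterion as "Increase in serum creatinine (up to 7 days) compared with baseline" and, in the same entry, adds that the rise has to take place within 48 hours. Urine output and renal replacement therapy are alternative routes to staging.

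**The concern.** The schedule plans two creatinine samples between the procedure and day 30. For early discharges the waiver reduces this to one, and nothing prevents that one from being drawn shortly after the procedure. By creatinine, stage II or III requires at least a doubling from baseline or, for one stage III route, a value of 4.0 mg/dl with an acute rise of at least 0.5 mg/dl. A sample taken within a few hours can show only what has happened by then. A rise that starts later may be clinically silent and may have resolved by day 30.

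At stake is the credibility of one named secondary safety rate in a single-arm registration study whose endpoints are reported descriptively. Under-detection runs in one direction, towards a lower observed rate.

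**Working it through.** The plan gives no calculated figure on this point, so the check is to set the time limits side by side.

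**Inputs**
- Post-Procedure window: up to 48 h, no earliest time (6.3.3.4).
- Waiver: applies to discharge within 48 h (6.3.3.5).
- Next scheduled creatinine: day 30 to day 44 (6.3.3.6, Table 3).
- Kidney-injury limits: 48 h and 7 days (section 10).

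**1. Gap between scheduled samples**
- With the waiver, the last sample lies between just after the procedure (day 0) and day 2. The gap runs from 30 − 2 = 28 days to 44 − 0 = 44 days.
- With the test repeated at a discharge at 48 h, the gap runs from 30 − 2 = 28 days to 44 − 2 = 42 days.
- The waiver therefore adds at most 44 − 42 = 2 days, which is about 48 h.

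**2. Can the 30-day sample stand in?**
- Earliest: 30 − 7 = 23 days after the 7-day limit. Latest: 44 − 7 = 37 days after it.
- It is outside both limits in section 10, so it cannot.

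**3. What one early sample covers.** As an illustration, assume a draw at hour 2 and discharge at hour 45.
- Observation given up by not sampling at discharge: 45 − 2 = 43 h.
- If the 48-hour condition is counted from the procedure, the sample leaves 48 − 2 = 46 h of that window unobserved. A draw at discharge would leave 48 − 45 = 3 h.
- Against the 7-day limit (7 × 24 = 168 h), the sample leaves 168 − 2 = 166 h unobserved. A draw at discharge would leave 168 − 45 = 123 h.
- A later draw is better on either reading. On the 7-day reading it closes only a small part of the gap.

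**4. Is timing controlled elsewhere?** The notes to Table 3 give hour limits for the cardiac enzymes. The first draw is within 8 h, then two more follow at 6 to 8 h intervals. The third draw falls between 0 + 6 + 6 = 12 h and 8 + 8 + 8 = 24 h. Creatinine is not tied to these draws.

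**5. How an unobserved case would be handled.** Section 11.4 has no rule for an endpoint that was not assessed, and section 11.5 leaves further detail to the SAP. The device-success entry in section 10 does treat an outcome as missing when the echocardiogram is missing or unevaluable. The kidney-injury entry has no counterpart.

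**The case against.** Several points against a broader complaint stand.

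- **The waiver does not cause the gap to day 30.** A reader might infer that it does. No patient has a visit between discharge and day 30, whenever discharge occurs, and the waiver accounts for at most about 48 h of the gap.
- **Discharge is not left unchecked.** The waiver covers only tests already collected Post-Procedure. The physical examination and the echocardiogram ("Comprehensive TTE. If not adequate, a TEE will be performed") are not on that list and remain due. Adverse-event review is also listed at discharge, and section 8.1 tells patients to contact the site about significant events between visits.
- **Extending the point to hemoglobin, conduction and neurological findings is not supported.** Conduction block is not a listed endpoint. The endpoint is permanent pacemaker implantation, which is a recorded intervention, and the rhythm text is only advice ("Up to 72 h, continuous rhythm monitoring is recommended"). Major bleeding requires overt bleeding, so a silent fall in hemoglobin does not qualify. Stroke is a clinical diagnosis and does not depend on a scheduled scale.
- **No rule says an unmeasured kidney injury is counted as absent.** That is a likely consequence of having no rule for missing assessments, but the documents do not state it.
- **Kidney injury has other routes.** Urine output and renal replacement therapy can establish it. Renal replacement would be recorded clinically. Urine output, however, is not on the Post-Procedure or Discharge lists or in Table 3, so it is an uncertain substitute.
- **The numbers are probably small.** Purely as assumptions, take 5% to 30% of 60 patients discharged early (3 to 18), a true stage II/III rate of 5% and no detection at all. The expected number missed is then 3 × 0.05 = 0.15 to 18 × 0.05 = 0.9, which is less than one patient.

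What survives is the creatinine route to kidney injury. Examination, echocardiography and self-report are poor ways to find a silent rise.

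**Conclusion.** The point holds for kidney injury alone. For patients discharged within 48 h, the plan as written allows a single creatinine with no earliest time to be the only scheduled sample inside either limit in section 10. Creatinine-defined stage II/III injury can therefore be under-detected in them, in the device's favour. This is true whichever of the two limits governs, and those two limits need to be reconciled in any case.

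No effect on the observed rate can be stated, because the documents do not give the share discharged within 48 h and it could be zero. In a cohort of 50 to 60, one missed case moves the rate by 1/60 = 1.7 to 1/50 = 2.0 percentage points. The primary endpoint is not affected. The point deserves action mainly because the remedy is cheap.

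**What to change.** In section 6.3.3.5, keep the waiver and add a sentence. The creatinine that serves both visits, and the blood count drawn with it, should be the last obtained before discharge, consistent with the existing weekend allowance, with its date and time in the eCRF. Any local creatinine available up to day 7 should also be entered.

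In section 10, reconcile the 48-hour and 7-day wording for kidney injury.

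In section 11 or the SAP, report kidney injury with the number assessed as denominator and show how many were not assessed. Treat it as missing, as device success already is, when no qualifying creatinine exists. This must not override injury already established by urine output or renal replacement therapy, which counts as an event.

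The cost is an occasional repeat blood draw at sites that also test early, plus one date-and-time field. Treatment and discharge decisions are untouched. The change does not close the gap between discharge and day 7. It moves the one scheduled sample as late as the stay allows and makes the remaining gap visible.
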